## *Western IRB Protocol*

**Protocol #:**

**Project Title:** The Point Digit: A Family of Ratcheting Prosthetic Finger Technology

**Principal Investigator:** [name]

**Version Date:** 8/2/2018

**I. Hypotheses and Specific Aims:** The purpose of this research is to study the use of passive prosthetic devices. The design of passive prosthetic devices for amputees will be tested by human subjects for strength, function, and durability. The hypothesis of the study asks whether certain design features can withstand activities of daily living. Examples of activities include lifting objects, pouring water, turning keys, etc.

**II. Background and Significance:** There are approximately 500,000 people living with minor upper limb loss in the USA [1],[2]. Minor upper limb loss (also partial hand amputation) is defined as the amputation of the bones distal to the wrist joint. While the field refers to these types of amputation as 'minor,' it can be a severe disability, especially if the amputation involves the thumb and/or multiple digits. In fact, partial hand amputees self-report a higher level of disability compared to other major unilateral upper limb amputees [3]. Furthermore, it was reported that fewer than half of partial hand amputees were able to return to the same job after amputation and most found that the prosthetic devices were insufficient to meet the demands of their work [4]. Amputation can cause physical, psychosocial, and economic damage to an individual and can lead to depression, anxiety, loss of self-esteem, and social isolation [5],[6]. While the number of individuals with partial hand amputation is 10 times more than all other categories of upper limb amputation combined, the state of available technology for this underserved patient population is relatively poor [7].

### **III. Preliminary Studies/Progress Report:**

### **IV. Research Methods**

#### **A. Outcome Measure(s):**

Outcome measures include completion rate, completion time, SHAP score, DASH score, box and blocks test, clothespin test, and other measures of function. These metrics quantify the performance of prosthetic devices.

#### **B. Description of Population to be Enrolled:**

The subject population will consist of a convenient sample of people. The subjects will have various ethnicity, age, and gender. An estimated total of 30 subjects will be enrolled. The subjects must be normal intact individuals and/or persons with amputation who are able to understand and follow directions in English, assessed by their ability to respond during the recruitment and consent process. Exclusion criteria include any subjects that are not able to understand the procedures and/or are less than 18 years of age.

#### **C. Study Design and Research Methods**

The experiments will take place at the Point Designs LLC headquarters, at partner clinics, and/or at home. The participant will come up to 3 times for up to 4 hour sessions. During this session the participant will be asked to perform activities of daily living in a laboratory setting. The only devices/materials coming into contact with the participant will be standard of care orthopedic/prosthetic equipment including gauze, casting tape, medical tape, prosthetic sockets. Risks from the above devices are possible minor skin discomfort. Standard of care procedures will be used to mount the prosthetic device. A training period will be followed by several tests to measure the function of the prosthetic device. Different versions of the device may be presented to the subject in a randomized order.

#### **D. Description, Risks and Justification of Procedures and Data Collection Tools:**

Risks from the above devices are possible minor skin discomfort. If you feel that you have been harmed while participating in this study, you should inform [name] at [contact] immediately.

#### **E. Potential Scientific Problems:**

Potential scientific problems include a lack of subjects with amputation and/or a lack of ability to perform the activities of daily living with the prosthetic devices.

#### **F. Data Analysis Plan:**

Data will be processed with standard statistical methods using MATLAB (Mathworks, Inc.) in order to produce the metrics described previously (completion rate, completion time, etc.)

**G. Summarize Knowledge to be Gained:**

The development of more functional/robust prosthetic devices will augment the quality of life for people with amputation.

## Statistical Power and Design

### Power calculation:

The primary outcome measure will be the improvement in intra-subject CAPPFUL scores while using the Point Digit system versus no prosthesis. CAPPFUL provides a full-scale score ranging from 0 to 100. The mean and standard deviation of CAPPFUL for partial hand amputees (n=17) is provided in [28] as  $71.37 \pm 10.15$ . If we consider a difference in CAPPFUL functional scores of one standard deviation (10.15) as clinically significant, a sample size of at least 11 subjects will be needed to reject the null hypothesis that the means are equal with power of 0.9 and a probability of Type I error of 0.05 (z-test for normally distributed data with known standard deviation). This sample size paired with the CAPPFUL metric will provide actionable evidence to support the Point Digit.

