### Data analysis:

Data will be gathered by Arm Dynamics and provided to the independent researchers at the Biomechatronics Development Laboratory. The data will be evaluated carefully by study team members without conflicts of interest to determine the distribution of all scores in the population studied and the variability of scores within and between uses of the two systems. We will measure the effectiveness of the *Point Digits* using the primary measures: CAPPFUL and WI. Both outcome measures will be studied over time by comparing the results across stage 0, 1, and 2. We hypothesize that the CAPPFUL and WI measures will increase from stage 0 to stage 2. Average scores across subjects will be studied using One-Factor ANOVAs to determine differences across the testing sessions. Post-hoc analysis (Tukey-Kramer post-hoc analysis) will be performed as necessary. One-sample t-tests will be used to compare the outcome measures with the existing dataset from Arm Dynamics. Pair-wised t-tests may be performed when a subject matches the demographic, functional, or psychological profiles of an existing subject within the dataset. Then, differences can be studied based on the prosthetic components, amputation level, or other subject attributes. A probability of Type I error of 0.05 will be used to determine statistical significance. Sex will not be a factor in this study.

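### The 0.9 power at 11 subjects comes from a known-SD z-test that fits neither the within-subject outcome nor the planned analyses; a two-sided paired t-test on the same inputs gives about 0.85

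*SAP*

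**What the plan says.** The SAP's Power calculation section defines the outcome as within-subject: "The primary outcome measure will be the improvement in intra-subject CAPPFUL scores while using the Point Digit system versus no prosthesis". For variability it relies on a published group: "The mean and standard deviation of CAPPFUL for partial hand amputees (n=17) is provided in [28] as" 71.37 ± 10.15. It then takes "a difference in CAPPFUL functional scores of one standard deviation (10.15) as clinically significant" and concludes that "a sample size of at least 11 subjects will be needed to reject the null hypothesis" of equal means, with power 0.9 and Type I error 0.05. The method is given as a "z-test for normally distributed data with known standard deviation". The section gives no SD of within-subject change, no within-subject correlation, and no statement of one- or two-sided testing.

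The SAP's Data analysis section plans four kinds of test:

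- One-factor ANOVAs over stages 0, 1 and 2: "Average scores across subjects will be studied using One-Factor ANOVAs to determine differences across the testing sessions".
- Tukey-Kramer comparisons after the ANOVAs, as needed.
- One-sample t-tests against an existing external dataset.
- Possible pairwise t-tests, in which a study subject is matched to a person in that dataset.

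No z-test appears there.

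**The concern.** The calculation that yields 11 differs from the outcome and the analysis in three ways.

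1. **The SD is not known.** It is an estimate from 17 people, and every planned test estimates the variance from data. With about 10 degrees of freedom, the gap between a z-test and a t-test is not negligible.
2. **The SD is of a different quantity.** Power for a within-subject improvement depends on the SD of the change. The 10.15 is described as the SD of scores in a group of people. Using it as the SD of change amounts to assuming a within-subject correlation of 0.5 with equal variances in both conditions. The SAP states neither.
3. **The sized comparison is not tied to a planned test.** No within-subject test of Point Digit versus no prosthesis is named. The ANOVAs compare three stages, and the pairwise t-tests compare study subjects with other people.

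The SAP presents this sample size as enough to give usable evidence for the device. If the result were null, a reader could not tell from the SAP which test had power 0.9, or whether any of them did.

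**Working it through.** **Inputs.** From the SAP's Power calculation section: difference δ = 10.15, SD = 10.15 (so δ/SD = 1), α = 0.05, power 0.9, n = 11. Sidedness is not stated. From the SAP's Data analysis section: the list of planned tests. Correlations and stage means below are assumptions, because the documents give none.

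**1. Reproducing the 11.** For a one-sample (paired) z-test, n = [(z for α + z for power) × SD/δ]².

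- Two-sided: (1.960 + 1.282)² = 10.51, rounded up to 11. Power at 11 is Φ(√11 − 1.960) = Φ(3.317 − 1.960) = 0.913.
- One-sided: (1.645 + 1.282)² = 8.56 with unrounded quantiles, rounded up to 9.

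The SAP's figure therefore reproduces exactly as a two-sided test, and the two-sided reading is inferred from this.

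**2. Same inputs, variance estimated.** For a two-sided paired t-test, power comes from the noncentral t distribution with n − 1 degrees of freedom and noncentrality √n × δ/SD of change. At n = 11 that is 10 degrees of freedom and noncentrality 3.317.

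| n | Power, two-sided paired t, δ = SD of change = 10.15 |
|---|---|
| 11 | 0.848 |
| 12 | 0.883 |
| 13 | 0.911 |

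Thirteen subjects are needed to exceed 0.90, two more than the SAP's 11.

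**3. What 0.90 at n = 11 requires.** Solving power = 0.90 with 10 degrees of freedom gives δ/SD of change = 1.0866.

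- At the SAP's difference, the SD of change must be no more than 10.15/1.0866 = 9.34.
- If the SD of change is 10.15, the detectable difference is 1.0866 × 10.15 = 11.03 points, not 10.15.

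**4. Dependence on the within-subject correlation ρ.** If both conditions have SD 10.15, the SD of change is 10.15 × √(2(1 − ρ)).

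| Assumed ρ | SD of change | Power at n = 11 |
|---|---|---|
| 0.3 | 12.01 | 0.71 |
| 0.4 | 11.12 | 0.78 |
| 0.5 | 10.15 | 0.85 |
| 0.6 | 9.08 | 0.92 |
| 0.7 | 7.86 | 0.97 |

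The limit of 9.34 from step 3 corresponds to ρ = 1 − (9.34/10.15)²/2, about 0.58.

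**5. The planned ANOVA, for illustration only.** Take n = 11, three stages, a one-SD rise from stage 0 to stage 2, and the middle-stage mean either halfway or equal to an end stage. The omnibus F-test has power 0.50 to 0.63 if stages are treated as independent groups (2 and 30 degrees of freedom). It has 0.79 to 0.90 as repeated measures with ρ = 0.5 (2 and 20 degrees of freedom, sphericity assumed). The conclusion does not rest on these values.

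**The case against.** The strongest reply has five parts.

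- **Eleven is a minimum.** The protocol's population section expects about 30 subjects. At an SD of change of 10.15, 13 amputees would give 0.91 and 15 would give 0.95. But those 30 may include people without amputation, so the number of amputees is not fixed. The 0.85 is correctly read as power at the stated minimum.
- **The 0.85 borrows the assumption it criticises.** This is fair. Only the step from z to t (0.913 to 0.848) follows from the SAP's own inputs. The rest is an unknown that may favour the trial: power is at least 0.90 once ρ is about 0.58 or more. The documents do not show that the trial is underpowered. They show that the stated power is unsupported.
- **A one-sided test would do.** The hypotheses are directional, and a one-sided paired t-test at 11 has power 0.924. But a one-sided z-test would have given 9, and the stated null is equality of means.
- **A planned test may already fit.** For the one-sample t-tests against the external dataset, with that mean treated as fixed, a between-person SD is the relevant one. If stage 0 is the no-prosthesis session, Tukey-Kramer would contain the contrast wanted. Neither link is stated. The one-sample comparison is also not the within-subject outcome, and both methods estimate the variance.
- **The ANOVA figures rest on assumed means, correlation and sphericity.** Agreed. They carry no weight in the conclusion.

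The Data analysis section also lists a second primary measure, WI. That is a separate matter and does not change this point.

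**Conclusion.** The concern holds. The power of 0.9 at 11 subjects belongs to a known-SD z-test that is not planned, using an SD that is not the SD of the outcome. The numerical effect that is certain on the SAP's own inputs is modest: about 0.85 instead of 0.90 at 11 subjects, or two more subjects to reach the target. The larger uncertainty is the unstated SD of change, which moves power between 0.71 and 0.97 for ρ from 0.3 to 0.7.

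This rests on a two-sided test (inferred from the reproduction), on reading 10.15 as a between-person SD (from the SAP's description, since the cited source was not available) and, for the table by ρ, on equal variances in the two conditions. It should be fixed, because the SAP relies on a power figure that is wrong as written for the outcome it defines.

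**What to change.** In the SAP's Power calculation section, replace the known-SD z-test statement with wording such as: *With 11 subjects, a two-sided paired t-test at alpha 0.05 has power of about 0.85 to detect a mean within-subject CAPPFUL change of 10.15, assuming that the SD of within-subject change is 10.15 (the published between-person SD; this corresponds to a within-subject correlation of 0.5 with equal variances).* Add one table row set: correlations of 0.3, 0.4, 0.5, 0.6 and 0.7 give power 0.71, 0.78, 0.85, 0.92 and 0.97. It would help to note that 13 subjects would give 0.91 under the same assumption.

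In the SAP's Data analysis section, name the two-sided paired (or repeated-measures) within-subject comparison of CAPPFUL with Point Digit versus no prosthesis as the primary test of the outcome that was sized.

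The cost is SAP wording in two sections and a less favourable stated power. No change to recruitment is requested.

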### Data analysis:

Data will be gathered by Arm Dynamics and provided to the independent researchers at the Biomechatronics Development Laboratory. The data will be evaluated carefully by study team members without conflicts of interest to determine the distribution of all scores in the population studied and the variability of scores within and between uses of the two systems. We will measure the effectiveness of the *Point Digits* using the primary measures: CAPPFUL and WI. Both outcome measures will be studied over time by comparing the results across stage 0, 1, and 2. We hypothesize that the CAPPFUL and WI measures will increase from stage 0 to stage 2. Average scores across subjects will be studied using One-Factor ANOVAs to determine differences across the testing sessions. Post-hoc analysis (Tukey-Kramer post-hoc analysis) will be performed as necessary. One-sample t-tests will be used to compare the outcome measures with the existing dataset from Arm Dynamics. Pair-wised t-tests may be performed when a subject matches the demographic, functional, or psychological profiles of an existing subject within the dataset. Then, differences can be studied based on the prosthetic components, amputation level, or other subject attributes. A probability of Type I error of 0.05 will be used to determine statistical significance. Sex will not be a factor in this study.

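### The SAP powers the trial on one primary outcome (CAPPFUL) but analyses two unranked ones (CAPPFUL and WI), with no rule joining them

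*SAP*

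**What the plan says.** The SAP's power calculation is singular and specific: "The primary outcome measure will be the improvement in intra-subject CAPPFUL scores while using the Point Digit system versus no prosthesis". It takes a 1 SD difference (10.15 points) as clinically significant. From power 0.9, a Type I error of 0.05 and a "z-test for normally distributed data with known standard deviation", it arrives at 11 subjects or more.

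The data analysis section of the same SAP assesses effectiveness "using the primary measures: CAPPFUL and WI", without ranking them. It continues: "Both outcome measures will be studied over time by comparing the results across stage 0, 1, and 2", and "We hypothesize that the CAPPFUL and WI measures will increase from stage 0 to stage 2". The methods are several. "Average scores across subjects will be studied using One-Factor ANOVAs to determine differences across the testing sessions", with Tukey-Kramer comparisons as needed. "One-sample t-tests will be used to compare the outcome measures with the existing dataset". Matched-pair t-tests are optional. On error it says only: "A probability of Type I error of 0.05 will be used to determine statistical significance".

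The protocol's outcome list (section IV.A) names neither CAPPFUL nor WI and ranks no outcome, so it cannot settle which section of the SAP governs.

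**The concern.** The two SAP sections disagree on how many primary outcomes there are, and nothing says how two would combine into a conclusion. The hypothesis that both will rise is an expectation; the SAP does not make it a success criterion. Tukey-Kramer adjusts for comparisons between sessions within one measure, not for having two measures. No listed test is designated primary, and the device-versus-no-prosthesis contrast in the power section is not linked to the three stages in the analysis section.

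A mixed result shows what is at stake. If WI is significant and CAPPFUL is not, one section says the trial missed its primary outcome, while the other allows a claim on a primary measure. The choice would then be made after the data are seen. Depending on the choice, either the stated power does not apply or the error rate is not the one intended.

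**Working it through.** **Inputs from the SAP.** CAPPFUL difference 10.15, SD 10.15 (standardised effect 1), power 0.9, alpha 0.05, n = 11, z-test with known SD.

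**Assumed, because the documents do not give them.** Correlation r between the CAPPFUL and WI test results, 0 to 0.9; WI effect, 1 SD or 0.5 SD; for the paired t-test, 10.15 as the SD of within-subject differences.

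**1. The plan's own figure.** n = (z for alpha + z for power)² / effect².
- Two-sided 0.05: (1.960 + 1.282)² = 10.51, so 11. This matches.
- One-sided 0.05: (1.645 + 1.282)² = 8.56, so 9. This does not match.

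The SAP does not state sidedness, but 11 is the two-sided answer. Power at n = 11 is Φ(√11 − 1.960) = Φ(1.357) = 0.913. The figure is correct for CAPPFUL alone. No effect size, SD or power is given for WI.

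**2. If both measures must succeed.** Error is at most 5%. Power is the probability that both tests are significant at n = 11. For the z-test at r = 0 it is the product of the two powers: 0.913 × 0.913 = 0.833 with a 1 SD WI effect. With 0.5 SD, WI power is Φ(0.5 × √11 − 1.960) = 0.381, and 0.913 × 0.381 = 0.348. The other z-test values come from the bivariate normal, and the joint paired-t values from simulation.

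| Test | CAPPFUL alone | WI effect | r = 0 | r = 0.5 | r = 0.9 |
|---|---|---|---|---|---|
| z-test | 0.913 | 1 SD | 0.833 | 0.852 | 0.884 |
| z-test | 0.913 | 0.5 SD | 0.348 | 0.374 | 0.382 |
| paired t | 0.848 | 1 SD | 0.719 | 0.750 | 0.802 |
| paired t | 0.848 | 0.5 SD | 0.275 | 0.307 | 0.321 |

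**3. If either measure suffices, each with a valid two-sided 0.05 test.** With neither measure truly changed and r = 0, the chance of at least one rejection in either direction is 1 − 0.95² = 0.0975. The chance of at least one falsely favourable result is 1 − 0.975² = 0.0494. The bivariate normal gives the rest.

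| r | Either direction | Falsely favourable |
|---|---|---|
| 0 | 0.0975 | 0.0494 |
| 0.3 | 0.0951 | 0.0476 |
| 0.5 | 0.0907 | 0.0454 |
| 0.7 | 0.0835 | 0.0417 |
| 0.9 | 0.0704 | 0.0352 |

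The single-test benchmarks are 0.05 and 0.05 / 2 = 0.025. Simulated paired t-tests at n = 11 agree: 0.097 to 0.072 in either direction, 0.049 to 0.036 favourable.

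**4. If either suffices and the test is the one-factor ANOVA across three stages.** Simulated with 11 subjects and two independent measures, at least one rejection:
- Ordinary ANOVA, which ignores that the same subjects are measured at each stage: 9.8%, 5.2%, 3.5%, 1.1% and 0.2% at within-subject correlation 0, 0.2, 0.3, 0.5 and 0.7.
- Repeated-measures ANOVA: 9.6% to 9.9% throughout.

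The excess error therefore also depends on which ANOVA is meant, and the SAP does not say.

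**The case against.** The strongest reply is that the power section settles the matter. It designates one outcome formally and closes by tying the evidence to CAPPFUL, so the later plural may mean no more than main measures. That reading is possible, but the word primary in the analysis section is then wrong and needs the same correction.

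A second reply is that the harm is conditional, and this stands in part. Inflation requires an either-suffices rule that the SAP does not state, together with tests that hold their level. Under an ordinary ANOVA with moderate within-subject correlation, the two-measure error falls below 5%. The 2.5% benchmark is inferred from the two-sided sample size and is not written in the SAP. Against a literal 0.05 for favourable results, 3.5% to 4.9% is not an excess. The either-direction figure does exceed 0.05, but it counts significant worsening as well.

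Third, the power losses rest on assumed WI effects. The 0.5 SD rows show sensitivity and are not evidence that the trial is underpowered for WI. With an equal 1 SD effect and the plan's z-test, the loss is modest: 0.913 to between 0.83 and 0.88.

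Finally, the stages may be defined in text that was not available for review, so the missing link between stages and conditions is not an established omission. The conflict between one and two primaries, and the absence of a joining rule, do not depend on any of these points.

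**Conclusion.** The concern holds. Two current sections of the SAP give conflicting primary designations; the sample size and power apply to only one of them, and no rule governs the other. The 11 subjects are correctly calculated for CAPPFUL under the stated z-test; the fault is that they do not cover WI or a joint decision. The size of the consequence depends on the missing rule. Requiring both costs power, by an amount set by the unknown WI effect. Accepting either can roughly double the nominal 2.5% chance of a falsely favourable result at worst, and may not raise error at all under an ordinary ANOVA. Confidence in the conflict is high. Because the effect is conditional and the repair cheap, this should be corrected before the data are examined, but it does not by itself invalidate the design.

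**What to change.** In the SAP's data analysis section:

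1. Make CAPPFUL the single primary outcome, in line with the power section.
2. Name one primary contrast, Point Digit versus no prosthesis, and state which stages supply each condition, or refer to where this is defined.
3. Name one within-subject test for that contrast, such as a two-sided paired t-test at 0.05.
4. Make WI the key secondary outcome, tested with the same contrast and test at 0.05 only if CAPPFUL is significant.
5. Label the remaining stage comparisons, the one-sample t-tests against the existing dataset and the matched-pair t-tests as supportive.

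With one contrast and one test per measure, this order holds the error across both measures at 5%.

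The cost is a few sentences. The planned 11 subjects and CAPPFUL's full 0.05 stay as they are. The drawback is that WI supports no confirmatory claim if CAPPFUL is not significant. Naming a paired t-test also makes visible that 11 subjects give CAPPFUL power of 0.85 rather than 0.9 if 10.15 is the SD of differences; 13 would give 0.91. That gap comes from the z-test in the power section, not from this change.

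If the sponsor wants WI to remain primary, a written both-must-succeed rule also controls error, but it needs a WI power calculation. Under the plan's z-test, and assuming a 1 SD effect on both measures, 0.9 joint power would take 13 subjects at correlation 0 or 0.5 and 12 at 0.8.

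### The SAP hypothesises a rise from stage 0 to stage 2 but plans no direct test of it; naming a paired contrast is a cheap improvement that can recover power

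*SAP*

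**What the plan says.** The SAP, under Data analysis, states one hypothesis about the stages: "We hypothesize that the CAPPFUL and WI measures will increase from stage 0 to stage 2". It also plans to study both measures by "comparing the results across stage 0, 1, and 2". The method for the stages is "One-Factor ANOVAs to determine differences across the testing sessions", and then "Post-hoc analysis (Tukey-Kramer post-hoc analysis) will be performed as necessary". No stage 2 minus stage 0 contrast is named, and neither is a subject term or a sphericity correction. The significance level is 0.05, with sidedness not stated.

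The t-tests in the same section do something else. The one-sample tests set the results against the Arm Dynamics dataset, and the pairwise tests are for matched subjects: "Pair-wised t-tests may be performed when a subject matches the demographic, functional, or psychological profiles of an existing subject within the dataset". The Protocol's Data Analysis Plan (IV.F) names no test that would fill the gap.

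The Power calculation section is built on a single comparison: "The primary outcome measure will be the improvement in intra-subject CAPPFUL scores while using the Point Digit system versus no prosthesis". It arrives at 11 subjects or more for power 0.9, with difference and SD both 10.15, from a z-test with known SD.

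**The concern.** The SAP knows in advance which comparison matters, yet leaves it to a follow-up step whose trigger is not defined. Three stages give three pairs. Tukey-Kramer corrects for all three, although only the 0–2 pair carries a stated direction. The sample size comes from one uncorrected within-subject test, so the test behind the 11 subjects is not the test in the analysis section. In a study this small, the difference can decide whether a real one-SD gain is declared.

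The plan also does not say which result would count as support for the hypothesis. The omnibus F-test asks only whether the stages differ in any way.

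**Working it through.** **Inputs from the SAP:** difference 10.15, SD 10.15, power 0.9, Type I error 0.05, n = 11, three stages.

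**Assumed, because the documents do not give them:** between-stage correlation ρ, equal SDs at each stage (unless stated otherwise), normality, and the stage 1 mean. The SAP quotes 10.15 as the SD of scores in 17 partial hand amputees, not as the SD of a change. With equal stage SDs, SD of change = 10.15 × √(2(1 − ρ)), which equals 10.15 only at ρ = 0.5.

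**1. The plan's own figure.** n = ((1.960 + 1.2816) × 10.15/10.15)² = 10.51, so 11. This reproduces with the two-sided one-sample z formula; power at 11 is 91.3%.

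**2. Planned paired test, n = 11, ρ = 0.5.** Noncentrality = √11 × 10.15/10.15 = 3.317 on 10 df. Two-sided power is 84.8%. The drop from 91.3% comes from estimating the SD and has nothing to do with this point.

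**3. F-test and Tukey with a subject term, same setting.** Error df = 2 × (11 − 1) = 20. An unadjusted pooled-error contrast (critical value 2.09) would have 88.4% power. The Tukey critical value, q(0.95; 3, 20)/√2 = 2.53, brings it to 77.7%. Requiring a significant F as well gives 76.4% to 77.5% by simulation, depending on the stage 1 mean. The loss against the paired test is about 7 to 8 points. Reaching 90% takes 13 subjects with the paired test and about 15 by this route.

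**4. Same route without a subject term.** Power is 43–45%. Most of that shortfall is due to the absent subject term, which is a separate and larger matter.

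**5. Other equal correlations** (n = 11, rise 10.15, subject term included):

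| ρ | Paired, two-sided | F then Tukey |
|---|---|---|
| 0.3 | 71–72% | 59–61% |
| 0.5 | 85% | 76–77% |
| 0.7 | 97% | 95% |

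**6. Unequal correlations** (order 0–1, 0–2, 1–2; subject term included). At 0.5/0.7/0.5, with the rise set to one SD of the change, the figures are 60% for F/Tukey and 85% for the paired test. At 0.5/0.5/0.9 they are 85–86% and 84–85%, so no loss. Where the 0–2 difference is the most variable, or among the most variable, the range is 82–90% against 85%. The pooled error then helps the Tukey pair.

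**7. Type I error with a subject term.** Equal correlations: F 4.9%, any pair 4.5%, 0–2 pair 1.9%. At 0.5/0.5/0.9: F 7.3% and any pair 6.7%, but the 0–2 pair about 4.7%. Across the markedly non-spherical cases tried: F 7.2–8.6%, 0–2 pair 4.7–6.9%. Without a subject term, F rejects in 0.1–3.0% of null trials. The paired test stays at 5% in the null cases simulated.

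**The case against.** The strongest reply is that the plan is not wrong in kind. It does intend to compare all three stages, and an omnibus test with all-pairs follow-up serves that aim. Tukey-Kramer needs no preceding F-test, so reading it as gated is an inference from "Post-hoc analysis (Tukey-Kramer post-hoc analysis) will be performed as necessary". The power loss depends on correlations that nobody has stated, and in some plausible patterns it is nil. All of this stands. It limits the size of the point but does not supply the missing contrast.

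Two stronger readings are tempting and should not be drawn.

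- **Inflated Type I error.** A reader might infer that the route inflates error for the hypothesised rise. It does not in general. Tukey controls error under equal correlations, the test is conservative if no subject term is fitted, and inflation needs marked, uncorrected non-sphericity. Even at 0.5/0.5/0.9 the 0–2 pair stays near 4.7%.
- **A false rise declared 90% of the time.** With a subject term and ρ = 0.5, F is significant in about 90% of trials where stage 1 gains one SD and stage 2 loses it again, and in 79% where scores fall by one SD. The SAP nowhere says that F alone would count as proof of a rise. In the first case, F followed by Tukey declares a 0–2 rise about 1% of the time. The figures show only that a significant F should not be read as showing the rise.

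It would also go too far to drop testing of the stage 1 comparisons. The visible text does not define the stages, so a comparison with stage 1 may bear on the device-versus-none question. Finally, the stage hypothesis is the SAP's and covers two measures; the Protocol's section I states a different one, on durability.

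**Conclusion.** The point holds as a cheap improvement. The SAP's stage hypothesis has no planned test of its own, and the analysis differs from the single test used for the sample size. At n = 11, a rise of 10.15 and equal correlation 0.5, this costs about 7 to 8 points of power once a subject term is fitted (85% against 76–78%). The cost is about 10 to 13 points at correlation 0.3 and about 2 at 0.7. Under unequal correlations it ranges from about 25 points to none, or a small gain. These figures are for CAPPFUL only, since the SAP gives no SD or target difference for WI. No claim is made about Type I error.

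**What to change.** In the SAP, Data analysis, add wording to this effect:

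> *For each measure, the primary test of the stage hypothesis is a paired t-test on each subject's stage 2 score minus stage 0 score, two-sided at 0.05, reported with a 95% confidence interval. It does not depend on an omnibus F-test. The three-stage comparison is secondary: an ANOVA with a subject term and a sphericity correction, with pairwise follow-up.*

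Two-sided testing matches the formula that reproduces the stated 11. The change is to wording only, with no new data. The price is that the stage 1 comparisons become secondary. The wording does not settle how two measures, each tested at 0.05, are to be handled together; that needs its own sentence.
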